**TOPSS: TOlerability of transcranial direct current stimulation in Pediatric Stroke Survivors**

**NCT05812794**

**Version Date: 07/20/2023**

**Protocol Title:** TOPSS: TOlerability of transcranial direct current stimulation in Pediatric Stroke Survivors

**Principal Investigator:** [name]

**Co-Investigators:** [name], PT.

**Study Coordinator:** [name], BSN. Research Nurse

**Population:** Patients who have arm weakness from a childhood stroke  
Sample size – 5  
Gender – male and female  
Age – 5 to 19 years of age  
Geographic location – near UTHealth Houston

**Number of Sites:** Single site – UT Health Houston

**Study Duration:** Expected Duration 1 year

**Subject Duration:** 3 months

---

#### **General Information**

- Stroke is defined as an abnormal blockage of a blood vessel or bleeding in the brain that leads to death of brain cells. Childhood stroke affects about 1 in 25,000 children every year and is a top 10 cause of disability in pediatrics. The purpose of this study will be to assess the tolerability of a rehabilitation technique referred to as Transcranial Direct Current Stimulation (tDCS) in childhood stroke survivors.

#### **Background Information**

- Hypothesis: tDCS will be well tolerated in childhood stroke survivors.
- **Background and Epidemiology:** Pediatric Stroke is a major neurologic problem that is among the top ten causes of death in pediatrics. Up to 75% of children suffer long-term neurologic impairment after stroke, with greater than one third suffering moderate to severe deficits years after their stroke. The 5 year direct medical costs of a single childhood stroke are over \$130,000 per patient. Given the large number of disability-years caused by a single childhood stroke, development of adjunctive treatments to traditional rehabilitation therapy for children with stroke is imperative. Transcranial direct current stimulation is an important neuromodulatory technique that holds promise in improving the outcome of patients with childhood stroke.
- Notably, pediatric stroke, defined as stroke occurring before the 18th birthday, is divided into two types; perinatal stroke and childhood stroke. Perinatal stroke includes intracerebral hemorrhage or arterial ischemic stroke occurring between 28 weeks gestation and 28 postnatal days of life, and 'childhood stroke' includes spontaneous intracranial hemorrhage and arterial ischemic stroke occurring between 28 days of life and 18 years of age. Childhood stroke occurs in approximately 1 in 25,000 children per year. This study will be of childhood stroke survivors with arm impairment.

- **Summary of prior safety data:** Transcranial direct current stimulation (tDCS) is a non-invasive neuromodulatory technique that has been studied extensively in adult stroke and has been subject of early efficacy trials in childhood cerebral palsy. This technique involves application of a small electrical current to the scalp during therapy sessions targeted at a specific impairment. The application of this small amount of current is thought to enhance neuroplasticity temporarily, and has shown benefit in motor learning in children and adults. A review safety paper in 2016 found that tDCS has been safe in adult and pediatric trials in the past. Modeling data from that paper suggested that the current used in human studies of tDCS was likely 2 orders of magnitude lower than the amount needed to induce damage to brain tissue. In cerebral palsy, a study analyzing adverse events in 119 children over 12 years found no serious adverse events. 58% had prior brain injury and/or epilepsy and 43 of the patients were perinatal stroke survivors. There were no seizures or major adverse events. Mild tingling/itching was reported in 37% of patients. Another study enrolled 13 patients with perinatal stroke, and also found no major adverse events, with similar rates of mild side effects.
- **Summary of prior efficacy data:** Importantly, 2 separate 2016 meta-analyses found treatment benefit in upper arm function for adult stroke patients receiving repeated sessions of tDCS vs sham. Due to these promising results in adult stroke, treatment-effect is currently under investigation in the NINDS-funded TRANSPORT 2 trial; a multicenter, Phase II, randomized, sham-controlled trial evaluating the effect of bihemispheric tDCS in adults with arm impairment after stroke. Efficacy in perinatal stroke is being investigated in the SPORT trial, with results likely to be published in the next 2 years.

### Objectives

- Primary objective: To evaluate the tolerability of tDCS in childhood stroke survivors.
  - Tolerability will be evaluated by
    - The percent of patients who are able to complete the study
    - The percent of patients that endorse mild side effects as documented on the 'Stimulation Monitoring Sheet' (included separately)
    - Monitoring of Peg-Board test results pre stimulation, post stimulation, and at the end therapy session
    - Monitoring of Vital Signs (pulse and blood pressure) pre stimulation, post stimulation, and at the end of the therapy session.
- Secondary Objectives: To assess for improvement in arm function in patients receiving tDCS and occupational therapy, 3 functional assessment visits will take place.
  - At each visit, the patient will complete the following:
    - Fugl-Meyer Upper Extremity Assessment
    - Canadian Occupational Performance Measure
    - Box and Blocks Test
    - Pediatric Stroke Outcome Measure
    - Melbourne Assessment of the Upper Extremity

### Outcome Measures:

- Tolerability Primary outcome measure:
  - Percent of patients who complete the study, as defined by patients who complete the 1-week post therapy assessment visit. Patients who voluntarily withdraw for any

- reason or who stop due to an adverse event will be defined as not completing the study.
- Tolerability Secondary outcome measures
  - Percent of patients that endorse mild side effects as documented on the stimulation monitoring sheet. The stimulation monitoring sheet is filled out during each stimulation session pre and post stimulation.
  - Percent of patients with hypotension or hypertension on blood pressure monitoring post stimulation and post therapy session. Time points for data collection will be pre-stimulation, post-stimulation, and post-therapy session.
  - Percent of patients with worsening of the Peg-board test (decreased score by 5 or greater) on the Peg-Board Test post stimulation and at the end of therapy session compared to baseline score. Time point will be the end of each therapy session.
- Improvement in Arm Function Primary outcome measure
  - Increase of 5 points or more on the Fugl-Meyer score of Upper extremity function at the 1 week post therapy assessment.
- Improvement in Arm Function Secondary Outcome Measure
  - Increase of 5 points or more on the Fugl-Meyer score of upper extremity function at the 3 month post therapy assessment.

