### **Study Design**

- This study is an unblinded interventional trial.
- Subjects will be childhood stroke survivors with chronic arm impairment, defined below in the inclusion and exclusion criteria. 5 patients total will be enrolled.

The Primary Objective is to assess tolerability of tDCS. Tolerability will be evaluated by

- The percent of patients who are able to complete the study
  - If any patients drop out due to tDCS related side effects, this would be considered poorly tolerated.
- The percent of patients that endorse mild side effects as documented on the 'Stimulation Monitoring Sheet' (included separately)
  - We expect 40% of patients to endorse mild side effects per session that will be non-treatment limiting.
- Monitoring of Peg-Board test results pre stimulation, post stimulation, and at the end therapy session to ensure no decrease (worsening) in score poststimulation.
- Monitoring of Vital Signs (pulse and blood pressure) pre stimulation, post stimulation, and at the end of the therapy session.
- Study description and sample timeline:
  - On enrollment, patients will have a study visit where they will have a Pediatric Stroke Outcome Measure completed by the PI as well as a medical history with the enrollment form. The study therapist will then complete the following assessments – Fugl-MeyerScore, Canadian Occupational Performance Measure, Box and Blocks test, Melbourne.
  - The patient will then come for 5 sequential days of 2 hour long occupational therapy sessions augmented by tDCS for the first 20 minutes of the session. At arrival, the "stimulation safety sheet" will be completed by the occupational therapist (form attached). The saline soaked electrodes will be placed on the study subjects head and connected to the

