Soterix 1x1 LTE enabled tDCS device. Prior to beginning stimulation, the "Investigator Screening Form" checklist will be completed for each patient during each stimulation. Current output through the device will be sham stimulation on day 1, followed by steady increases to a maximum of 1mA in patients aged 5-12 years old, and 1.5mA in patients aged 13-19 years old, per the study design flow sheet at the end of this protocol. The child and parents will be blinded to the sham stimulation. The investigators will not be, since all patients receive the same age based current protocol. Consequently, investigators will be aware it is sham stimulation on day 1. We have chosen to have sham stimulation on the first day to acquire baseline data for tolerability and reported side effects without current being passed through the electrodes, which we will report with descriptive statistics. Blood pressure, pulse rate, and peg-board scores will be recorded as indicated on the stimulation safety sheet during each session.

- A repeat assessment will be done by the occupational therapist one week post therapy completion.
- There will be a repeat assessment visit 3 months post intervention.

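### Mild side effects have no stated record after the post-stimulation entry, so late symptoms that resolve before the next entry can go uncounted in the secondary side-effect percentage.

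*Combined protocol and SAP*

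**What the plan says.** The share of children with mild side effects is one of the measures listed for the primary objective (Objectives; Study Design). Outcome Measures classes it as a secondary tolerability outcome: "Percent of patients that endorse mild side effects as documented on the stimulation monitoring sheet". The timing follows directly: "The stimulation monitoring sheet is filled out during each stimulation session pre and post stimulation".

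The other tolerability measures have a third time. For blood pressure, Outcome Measures states: "Time points for data collection will be pre-stimulation, post-stimulation, and post-therapy session". Objectives has "Monitoring of Vital Signs (pulse and blood pressure) pre stimulation, post stimulation, and at the end of the therapy session" and "Monitoring of Peg-Board test results pre stimulation, post stimulation, and at the end therapy session".

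Study Design describes the treatment week as "5 sequential days of 2 hour long occupational therapy sessions augmented by tDCS for the first 20 minutes of the session". Day 1 is sham, so as to "acquire baseline data for tolerability and reported side effects without current being passed through the electrodes".

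For the 1-week and 3-month visits, Study Procedures lists functional tests and a neurologic examination, with no symptom question. Data and Safety Monitoring commits to watching for mild side effects such as headache but gives no times. The monitoring sheet is described as included separately and is not in the available text.

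**The concern.** The protocol treats the end of stimulation and the end of the session as different moments, and gives symptoms only the earlier one. Headache is among the expected mild effects and need not begin while current is flowing. A child whose headache starts during therapy or that evening, and has gone by the next morning, has no stated place on the record. Day 5 is the weakest point: it ends a week in which current is raised stepwise, and no next-day sheet follows it.

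At stake is how complete the symptom data are in a study whose purpose is tolerability, and how the reported percentage should be read.

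**Working it through.** **1. Time points side by side**

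| Measure | Pre-stimulation | Post-stimulation | End of session | Source |
|---|---|---|---|---|
| Symptoms | yes | yes | not stated | Outcome Measures |
| Blood pressure | yes | yes | yes | Objectives, Outcome Measures, Study Design |
| Pulse | yes | yes | yes | Objectives, Study Design |
| Peg-Board | yes | yes | yes | Objectives, Study Design |

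**2. Time without a stated symptom entry.** Inputs from Study Design: session 120 minutes, stimulation 20 minutes, 5 sessions.

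- Per session: 120 − 20 = 100 minutes; 100/120 = 83%.
- Over the week: 5 × 100 = 500 of 5 × 120 = 600 minutes.
- In addition: the hours between sessions, and everything after day 5.

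The 83% is a share of clock time. It is not the share of symptoms lost.

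**3. Which symptoms are counted under the rule as written**

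- Present at the post-stimulation entry: counted.
- Late onset on days 1 to 4, still present the next morning: counted, because it is endorsed at the next pre-stimulation entry and no rule discounts such entries.
- Late onset on days 1 to 4, resolved by the next morning: recorded only if volunteered, since no recall question is stated.
- Late onset on day 5: no later entry is stated.
- Present before stimulation, or on the sham day: counted, because no rule excludes it.

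The third and fourth cases can only lower the percentage. The fifth can raise it. The net sign is therefore not determined.

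**4. Size.** The plan gives no calculation for this outcome; Statistics specifies description only, with n = 5. One child is 1/5 = 20 percentage points. The outcome is per patient, so a child is lost only if no entry at any of the five sessions records a symptom.

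**5. Illustration, resting on an assumption.** Let f be the share of affected children whose symptoms all escape the stated entries. The documents give no value for f. Take 40% as the true per-patient proportion (Data and Safety Monitoring), ignore the upward sources in step 3, and treat the children as independent. The recorded proportion is p = 0.40 × (1 − f), and the chance that none of five children is recorded is (1 − p)^5.

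| f (assumed) | p | Expected children of 5 | Chance none recorded |
|---|---|---|---|
| 0 | 40% | 2.0 | 0.60^5 = 7.8% |
| 10% | 36% | 1.8 | 0.64^5 = 10.7% |
| 25% | 30% | 1.5 | 0.70^5 = 16.8% |
| 50% | 20% | 1.0 | 0.80^5 = 32.8% |

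This shows sensitivity to f and is not an estimate. The starting value is itself unclear: Study Design gives the expected 40% per session, Data and Safety Monitoring gives it per patient. If sessions were independent (an assumption), 40% per session would mean 1 − 0.60^5 = 92% of children over five sessions, or 1 − 0.60^4 = 87% over the four active ones.

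**The case against.** The strongest reply is that the form is unseen. Attachments lists only two day-of-stimulation forms, a screening sheet and a safety sheet. The monitoring sheet may be that safety sheet, which carries blood pressure, pulse and Peg-Board for each session and so may already have an end-of-session entry. The therapist is with the child throughout the session, and the commitment to monitor for headache has no time limit. Because the outcome is per patient, one endorsement at any entry is enough to count the child.

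Much of this stands: it lowers confidence and rules out any claim that late symptoms are certainly missed. It does not remove the point. The timing is stated in the body of the protocol, and Study Design names only the three physical measures for the safety sheet. If the sheet does ask at the end of the session, Outcome Measures is wrong and needs correcting.

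A reader might also draw four stronger conclusions that the documents do not support:

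- *A headache lasting to the next morning would be dismissed as unrelated.* The outcome has no attribution step and does not subtract pre-stimulation entries, so that child counts.
- *The percentage is biased downward overall.* The missing late entries act downward, but pre-existing and sham-day symptoms act upward.
- *Tolerability as a whole will look better than it is.* The primary outcome is completion to the 1-week visit, and stopping for an adverse event counts against it. Study Design defines poor tolerability by dropout from tDCS-related side effects. Neither uses this percentage, which has no threshold.
- *Delayed symptoms are withheld from the DSMB.* Case report forms go to the board after the 1-week visit, and their content is not shown.

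**Conclusion.** The gap is real but limited. It concerns the secondary mild side-effect percentage and the completeness of symptom data. Symptoms that begin after the post-stimulation entry and resolve before the next one, and any that begin after the day 5 entry, have no stated point of capture. How many children this affects cannot be derived from the documents.

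The conclusion assumes that post stimulation means the moment after the 20 minutes and not the end of the session. The separate end-of-session label for the other measures supports that reading. It also assumes that the unseen sheet follows the stated timing. The change is worth making because it is cheap and improves a listed tolerability measure.

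**What to change.** Amend Outcome Measures as follows, and align the sheet:

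1. Complete the symptom items a third time at the end of each therapy session, when the other measures are already taken.
2. Add one item, *any symptom since the last session*, to the next day's pre-stimulation entry and, for day 5, to the 1-week visit. Record when the symptom began.
3. Define the outcome as symptoms new or worse than that session's pre-stimulation entry, plus recalled symptoms attributed to the preceding session. Adopt this together with item 2: a new-or-worse rule alone would drop the symptoms that persist to the next morning, which are counted now.
4. Report the sham day and the active days separately, and state whether the percentage is per patient or per session.
5. If the sheet already has an end-of-session entry, correct the text to match it.

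The cost is a few minutes per session for a therapist who is already present, and one question at an existing visit. The reported percentage may rise and will include some symptoms unrelated to stimulation, particularly those recalled over the week after day 5. Sample size and number of visits do not change.

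### The blood-pressure outcome leaves out the same-session pre-stimulation reading and does not separate sham day 1, so a reading unrelated to current can be reported as an event

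*Combined protocol and SAP*

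**What the plan says.** All references are to the combined protocol and SAP.

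- **Outcome Measures, tolerability secondary outcomes.** The blood-pressure outcome is the "Percent of patients with hypotension or hypertension on blood pressure monitoring post stimulation and post therapy session". The next sentence adds: "Time points for data collection will be pre-stimulation, post-stimulation, and post-therapy session". The pre-stimulation value is thus collected but not used in the definition. The peg-board outcome that follows is assessed "on the Peg-Board Test post stimulation and at the end of therapy session compared to baseline score".
- **Objectives (repeated in Study Design).** The primary tolerability objective includes "Monitoring of Vital Signs (pulse and blood pressure) pre stimulation, post stimulation, and at the end of the therapy session". Outcome Measures lists no pulse outcome.
- **Study Design.** "Current output through the device will be sham stimulation on day 1", and current then rises over the remaining four days. The reason given is: "We have chosen to have sham stimulation on the first day to acquire baseline data for tolerability and reported side effects". Results from that day are to be summarised descriptively. Blood pressure and pulse are recorded in each session on the stimulation safety sheet. For the Investigator Screening Form, a "checklist will be completed for each patient during each stimulation". Neither form is in the supplied text.
- **Study Population.** None of the three exclusion criteria mentions blood pressure.
- **Data and Safety Monitoring.** Hypotension and tachycardia are monitored, and no patient is expected to develop either. Hypertension is not named.
- **Statistics.** Five patients, descriptive statistics only, all subjects included.

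**The concern.** The outcome should help a reader judge whether stimulation disturbs blood pressure. As worded it records whether a child was out of limits after stimulation or after therapy, whatever the pressure was beforehand and whether or not current was passed. Two kinds of child can be counted with no effect of current: one already out of limits on arrival and unchanged afterwards, and one out of limits only on sham day 1. With five children, either makes the published figure 20%. The readings that would tell these children apart from a new event are already planned.

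There is a smaller problem of alignment. Pulse belongs to the primary objective and has an expected result (no tachycardia), but no listed outcome reports it. Outcome Measures names hypotension and hypertension; Data and Safety Monitoring names hypotension and tachycardia.

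**Working it through.** The plan gives no rate, threshold or derivation for this outcome, so there is no figure of its own to reproduce.

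**Inputs from the documents.** 5 children; 5 sessions each (1 sham, 4 active); 3 readings per session, of which 2 are later readings. One child is 1/5 = 20%.

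**Assumptions.** q is the chance that any one reading is out of limits with no effect of stimulation, and r = 1 − q. Readings are independent unless stated. A child counts if either later reading on any day is out of limits; the plan does not state this rule. q = 1%, 5% and 10% are illustrative.

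**1. Counted as worded.** 1 − r^10. At 5%: 1 − 0.95^10 = 40.1% of children. Chance of at least one of five: 1 − 0.95^50 = 92%.

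**2. Counted on sham day only.** (1 − r²) × r^8, and for at least one of five, 1 − (1 − x)^5.

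| q | Per child (x) | At least one of five |
|---|---|---|
| 1% | 1.8% | 9% |
| 5% | 6.5% | 28% |
| 10% | 8.2% | 35% |

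With a latent-normal within-child correlation of 0.5 at q = 5% (simulation of 1,000,000 children), these become 2.7% per child and 13% for any of five.

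**3. Effect of the change on random flags, like for like (either later reading, q = 5%).**
- Active days only: 1 − 0.95^8 = 33.7%.
- Active days and new onset: the chance per session is 0.95 × (1 − 0.95²) = 0.0926. Over four days this is 1 − (1 − 0.0926)^4 = 32.2%.
- At least one of five: 1 − (1 − 0.0926)^20 = 86%, against 92% as worded.

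Most of the fall from 40.1% to 32.2% comes from setting the sham day apart. For random flags the new-onset condition adds little.

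**4. Effect for a child persistently out of limits.** Let h be that child's out-of-limits rate per reading. As worded, the chance of being counted is 1 − (1 − h)^10, above 99.9% for every h below. New onset on either later reading over four active days has chance n = (1 − h) × [1 − (1 − h)²] per session and 1 − (1 − n)^4 overall.

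| h | n | New-onset count |
|---|---|---|
| 80% | 0.192 | 57% |
| 90% | 0.099 | 34% |
| 95% | 0.0499 | 19% |
| 100% | 0 | 0% |

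This is where the change matters.

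**5. Effect of the unstated combination rule.** If both later readings in a session must be out of limits, the as-worded figure at q = 5% is 1 − (1 − 0.05²)^5 = 1.2%, not 40.1%. The sham-only figure becomes 0.05² × (1 − 0.05²)^4 = 0.25%, not 6.5%. This rule moves the result more than either change in step 3.

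**The case against.** **Sham-day data are already promised.** Study Design says tolerability data from the sham day will be described, and vital signs are part of tolerability. A reader might infer from the outcome wording that the sham day goes unused; the documents do not support that. What remains is that the blood-pressure percentage does not carry the split over.

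**The peg-board contrast is weak.** Worsening is a change and needs a comparator, while hypotension and hypertension are states that can be judged against limits. The peg-board baseline is also not defined as the same-session value. This stands: the contrast shows that the plan names a comparator elsewhere, not that a same-session convention exists. The point rests on the blood-pressure definition itself.

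**The unseen forms may deal with it.** They may hold limits, pre-session checks or a comparison with the earlier reading. It would therefore be wrong to infer that the trial has no limits, or that a child out of limits on arrival would certainly be stimulated and counted. Even so, the outcome should state its reference reading and which days count. The expectation that no patient will develop hypotension suggests new onset, but it omits hypertension and is not part of the outcome.

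**The gain is small and nothing turns on it.** For random flags this is right (step 3), and nothing in the documents says that a persistently out-of-limits child is likely. A reader might expect the change to remove chance flags or to allow attribution to tDCS. It does neither: there is one arm, and sham is always first.

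**Pulse is not lost.** A reader might infer that pulse is unmonitored. It is recorded each session and tachycardia is watched for; only a listed outcome is missing.

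**Conclusion.** The point holds as a cheap improvement of modest importance. The outcome as worded can report a child as an event, 1 of 5 or 20%, because of a state present before stimulation or a reading on a day without current, subject to what the unseen forms contain. A same-session new-onset count with the sham day shown apart answers the tolerability question more directly, using readings already planned.

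The 20% follows from the sample size. Every other rate rests on assumed out-of-limits frequencies, on independence except where correlation is stated, and on the either-reading, any-day rule. The benefit is mainly for a child persistently out of limits. The outcome is secondary and descriptive, and a reader should not infer that a miscounted child could halt the trial: the Statistics section ends it only for a major safety event that the DSMB attributes to the intervention. The pulse point is a minor alignment.

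**What to change.** 1. Keep the existing blood-pressure count, and state whether a child counts on either later reading or only on both, and whether any single day suffices.
2. Using the sponsor's own limits, report beside it a new-onset count: within limits before stimulation and outside them later in the same session. Show post-stimulation and post-therapy separately.
3. Tabulate active days 2–5 (5 × 4 = 20 sessions if all are completed) apart from sham day 1 (5 sessions). State that sham is always the first day, so the comparison is descriptive and confounded with visit order.
4. List all readings of any child out of limits before stimulation. Such a child cannot enter the new-onset count for that session, and worsening must stay visible.
5. Report the pulse already recorded among the tolerability outcomes, and reconcile Outcome Measures with Data and Safety Monitoring on which vital-sign events are tracked.
6. State that isolated flags are expected by chance and will remain.

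The cost is wording and some extra tabulation. Pressure and pulse are already planned at all three time points, so no new measurement or change in sample size is needed. The downside is two counts where there was one.

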### **Statistics**

- As this is a 5 patient tolerability study, only descriptive statistics will be used.
- 5 patients total will be enrolled, and results will be reported with descriptive statistics.
- The trial will be terminated if there is a major safety event deemed to be due to the intervention by the DSMB.
- All subjects will be included in the descriptive analysis.

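### The only Peg-Board outcome is the percent of five children with a drop of 5 or more, with no numeric summary of change planned, so a 4-point loss in every child reads as 0% worsened

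*Combined protocol and SAP*

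**What the plan says.** Outcome Measures lists, among the secondary tolerability outcomes, "Percent of patients with worsening of the Peg-board test (decreased score by 5 or greater", to be assessed "post stimulation and at the end of therapy session compared to baseline score". The next sentence adds "Time point will be the end of each therapy session". This is the only Peg-Board outcome defined.

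Study Design states the purpose: "Monitoring of Peg-Board test results pre stimulation, post stimulation, and at the end therapy session to ensure no decrease (worsening) in score poststimulation". That aim has no 5-point margin. On collection, the same section says "Blood pressure, pulse rate, and peg-board scores will be recorded as indicated on the stimulation safety sheet during each session". It also sets the number of sessions ("The patient will then come for 5 sequential days of 2 hour long occupational therapy sessions") and makes the first one different: "Current output through the device will be sham stimulation on day 1".

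The Statistics section says "As this is a 5 patient tolerability study, only descriptive statistics will be used". It names no mean, median, range or listing of Peg-Board change.

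Four things are left open:
- which score is the baseline (the Peg-Board is not among the enrolment-visit tests in Study Design or Study Procedures);
- whether one session is enough to count a child, or each session gets its own percent;
- whether one or both later readings must fall;
- whether the sham day counts.

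**The concern.** The stated aim and the reported quantity do not match. The aim is to see that scores do not fall. The outcome records only falls of 5 or more, in five children, where one child moves the result by 20 percentage points. Any smaller loss is invisible in the planned result, however consistent it is across children and sessions.

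The Peg-Board is the study's objective before-and-after check on short-term hand function around stimulation. A published 0% worsened would be read as reassurance, and the planned summary cannot separate no change from a steady loss just under the cut. Conversely, if a single low reading is enough to count a child, ordinary test-retest variation could produce a worsening rate that says nothing about stimulation.

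**Working it through.** The plan gives no Peg-Board SD, expected rate or justification of the cut, so there is no stated figure to reproduce.

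**1. Size of the data.** Five sessions × 2 later readings = 10 changes per child, and 5 children × 10 = 50 changes in all. Per child, 2 belong to sham day 1 and 4 × 2 = 8 to active days. A percent of five children moves in steps of 1/5 = 20 points.

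**2. A case that needs no assumption about variability.** Let every later reading in every child be 4 points below whichever baseline is used. A child counts only if the change is −5 or lower.

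| Reading of the rule | Reported result |
|---|---|
| Any reading in any session | 0/5 = 0% |
| Both readings in the same session | 0/5 = 0% |
| A separate percent for each session | 0% at all five sessions |
| Mean change over the child's sessions | 0/5 = 0% |

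The numeric summary would be a mean change of −4.0 in each child. By contrast, a child with one end-of-session change of −5 and four of 0 has a mean of −5/5 = −1.0, yet counts as worsened under an any-session rule (1/5 = 20%).

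**3. False flags with no true change.** Assumptions:
- the SD of a single change is 2, 3 or 4 points;
- errors are normal and sessions independent;
- changes are in whole points, so a drop of 5 or more means an underlying change of −4.5 or lower;
- both later readings are compared with the same pre-stimulation score, so the two changes in a session correlate at 0.5.

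One reading is flagged with probability p = Φ(−4.5/SD). Both readings in a session are flagged with probability p₂ (bivariate normal, correlation 0.5). At least one is flagged with probability q = 2p − p₂. Over five sessions the any-of-10 rule gives 1 − (1 − q)⁵, and the both-readings rule gives 1 − (1 − p₂)⁵.

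| SD of change | p | p₂ | q | Any of 10 | Both in one session |
|---|---|---|---|---|---|
| 2 | 0.0122 | 0.0017 | 0.0227 | 11% | 1% |
| 3 | 0.0668 | 0.0183 | 0.1153 | 46% | 9% |
| 4 | 0.1303 | 0.0472 | 0.2134 | 70% | 22% |

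Without whole-point rounding, the any-of-10 figures are 6%, 36% and 62%. At SD 1 they are 0% either way. The false-flag rate therefore depends heavily on a rule the plan does not state.

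**4. The two failures do not occur together.** Take a true constant drop of 3 and count any of the five end-of-session readings. Without rounding, the chance that none of the five children is flagged is (1 − p)²⁵ with p = Φ(−2/SD):
- SD 1: p = 0.0228, giving 0.9772²⁵ = 56%.
- SD 2: p = 0.1587, giving 0.8413²⁵ = 1%.

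With whole-point rounding, p = Φ(−1.5/SD):
- SD 1: p = 0.0668, giving 0.9332²⁵ = 18%.
- SD 2: p = 0.2266, giving 0.7734²⁵ = 0.2%.

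Under an any-session rule, losses below the cut are missed mainly when scores are stable, and false flags arise mainly when scores vary.

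**The case against.** **The sessions may not be collapsed.** A reader might infer that each child's five sessions become a single yes/no. Outcome Measures does not say so. Its time point allows a separate percent per session, and Study Design words its side-effect expectation per session. This stands. What the plan lacks is a stated rule, and step 2 gives 0% either way.

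**The scores are not thrown away.** They are recorded at every session. Case report forms go to the DSMB after each child's 1-week visit, and the DSMB must approve before the next child starts (Data and Safety Monitoring). The Statistics section does not forbid numeric summaries. This also stands, so the point is about what is pre-specified for reporting, not about lost data or unmonitored children.

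**A reader might infer a large loss of power.** Take a true mean drop of 2, four active sessions and a between-child SD of 0.5. A one-sided 5% t test on the five child means then detects the drop in 99%, 94%, 75% and 56% of simulated trials at change SDs of 1.5, 2, 3 and 4. A count of flagged children detects it in 67%, 61%, 33% and 17%. The documents do not support using this against the plan, which has no test, alpha or count threshold. Much of the gap at the larger SDs also comes from the count rule's smaller type I error. With sizes matched, the figures are 98% vs 67%, 85% vs 61%, 44% vs 33% and 26% vs 17%. At a between-child SD of 1 with change SD 1.5 or 2, the gap vanishes or reverses.

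**A percent worsened is an ordinary tolerability summary, and a mean can mislead too.** Current rises over the active days, so averaging them can hide one child's fall at a single step. This is right, and it is why an individual listing should come before any average.

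**Conclusion.** The point holds as a gap between aim and outcome. The plan's only Peg-Board result is a 5-point cut in five children, and it reports 0% for a 4-point loss at every reading in every child. That conclusion rests on no assumed variability and on no particular reading of the rule.

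The false-flag figures (about 11%, 46% and 70%) are conditional on an any-of-10 rule and assumed change SDs of 2, 3 and 4. The text gives neither the Peg-Board's version and range nor its variability, so neither failure can be shown to apply here, and whether 4 points is a clinically important loss cannot be judged. The documents do not support saying that the data are discarded, that each child is reduced to one flag, or that the trial loses a given amount of power.

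Severity is minor to moderate: this is a secondary tolerability outcome in a descriptive study, and the remedy is cheap.

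**What to change.** In Outcome Measures, define the Peg-Board outcome as the numeric change from the same session's pre-stimulation score, both to the post-stimulation reading and to the end-of-session reading. List it for every child and session, with sham day 1 shown apart from the active days. Summarise it with the group mean or median and the range. A per-child mean over active days and an interval may be added as description only, since no test is planned.

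Keep the percent with a drop of 5 or more as a supporting summary. State its baseline, which readings and sessions count, whether sham day 1 is included, and its denominator. Reconcile the 5-point cut with the aim of no decrease in Study Design.

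The cost is one sentence and one table, from scores already collected, with no new visits or patients. The downside is a less compact result, with wide uncertainty at n = 5.
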